3.3. Compliance to treatment

Compliance to treatment will be monitored by the analysis of systemic fatty acid profiles at the end of the study (180 days) from baseline.

Assessment of the return of unused capsules at follow-up visits, for counting by an independent research assistant, will also be used to monitor compliance to treatment.

3.4. Concomitant medications and care

Concomitant medications and care, including insulin pumps, with a start date \geq 3 months prior to Visit 1 are permitted during the study.

Aspirin use is permitted during the study. Other blood thinning medications (e.g., warfarin, enoxaparin, dipyridamole, clopidogrel) are not permitted; participants taking these medications will not be eligible to participate in the study.

nPROOFS1-v1.2 [01-July-2018] Page 10 of 53

Participants will be asked to maintain their current dietary habits throughout the study and notify the study investigators of any major dietary changes.

3.5. Storage of study product

The study product will be stored in the [name] Laboratory, within the Department of Optometry and Vision Science at the University of Melbourne, in a secure (locked) area, at room temperature (20° to 25° Celsius, in a controlled chamber). Study products will be administered only to participants who have enrolled in the study, at no cost to the participant, in accordance with the conditions specified in this protocol.

3.6. Study product inventory

A detailed inventory will be kept for the study products (e.g., date of dispense, randomisation number, by whom, date of return and accountability of capsules. Study product will only be dispensed by an appropriately-qualified study personnel member. The study product is to be used in accordance with the protocol by participants.

3.7. Assignment of Interventions

3.7.1. Method of masking

Implementation of study allocation protocols will be conducted by an independent data manager. All trial participants and study investigators, including outcome assessors and data analysts, will be masked from the participant allocation.

Oral supplements will be packaged into identical opaque containers by a compounding pharmacist (Dartnell's Pharmacy, Surrey Hills, Victoria), to maintain double-masking. Participants' adherence to treatment will be monitored at follow-up visits by assessment of returned unused capsules by an independent researcher.

The investigators involved in the collection and analysis of data will not be involved in the reconciliation of returned study products, to maintain masking.

3.7.2. Unmasking the study product

During the trial, only when necessary for the safety and proper treatment of a participant, is it permissible for the principal investigator to request the independent data manager to unmask the participant's treatment assignment, to determine which treatment has been assigned, and institute appropriate follow-up care.

Only the principal investigator, following consultation with the independent data manager, is authorised to perform an unmasking procedure. The reason for breaking the code must be recorded in the participant's source documents.

3.7.3. Treatment allocation ratio and method of participant randomisation

A randomised allocation sequence will be generated, in advance, by the independent data manager, using Microsoft Excel, to assign equal numbers of participants in the treatment and placebo groups.

The randomisation schedule will be kept by the independent data manager and will be provided to an independent entity (i.e., compounding pharmacist) for labelling of the investigational product, in sequential order, to a corresponding participant number.

Eligible participants will be enrolled and assigned, by the sequential participant number, to either the treatment group or the placebo group, the treatment allocation for which will not be known to the study personnel who was involved in enrolment (i.e., the study investigator) or the participant.

4. Participant's timeline and schedule of study visits

4. Participa		lemme	and S	ciicuu	10 01 3	tuuy v	13163			
Test	Repeats	Visit 1 (Day -35)	Visit 2 Day: 1	Visit 3 Day: 30±14	Visit 4 Day: 90±14	Visit 5 Day: 180+/ 24	Visit 6 Day: 180+/ 24	Notes	Time Expected (mins)	Location
Location		UoM	SVH	UoM	UoM	SVH	UoM			
Eligibility Determination										
PICF	-								20	_
Demographics	-									
Medical History	-							Medications, concurrent procedures		
Ocular History	-								10	
Adverse Events	-								1	
Diet Inquiry	-									
Pregnancy Test	-							Females of childbearing potential only	10	
Habitual VA	-								5	
			Ar	iterio	r Eye I	Health	l			
MNSI questionnaire										-
OSDI Questionnaire	-								5	University of Melbourne
EQ-5D-5L questionnaire										f Melb
iMTA questionnaire										sity o
Tear Osmolarity										niveı
Non-contact aesthesiometry	Central							Double-staircase threshold		U
	Inferior								20	
Cooled threshold	Central								_,	
	Inferior								 	
Basal tear collection									15	
Phenol red thread test										
		1		Sl	it lamp		1			
Slit lamp exam										
Anterior chamber VH grading	-							Assessment of anterior chamber angle	5	
	Instill NaFl									
NaFl TBUT										

Test	Repeats	Visit 1 (Day -35)	Visit 2 Day: 1	Visit 3 Day: 30±14	Visit 4 Day: 90±14	Visit 5 Day: 180+/ 24	Visit 6 Day: 180+/ 24	Notes	Time Expected (mins)	Location
Location		UoM	SVH	UoM	UoM	SVH	UoM			
NaFl staining	Cornea							Mag 16X, Max Intensity, Blue Light, Wratten filter Oxford Grading Scale		
Instill topical anaesthetic										
IOP								Goldmann tonometer	5	
		till myd								
Corneal confocal microscopy	(Antra)									-
мегозсору	Inferior								10	ourn(
	Systemic fatty acid level analysis									
Blood pin-prick test							j		5	University of Melbourne
			Re	tinopa	athy G	radin	g			
Retinal imaging	Right								- 10	Univ
	Left									
Recheck eligibility										
		ı		Rand	omisa	tion				
Randomisation	-									
Dispense study supplements	-								5	
Collection of unused supplements	-		D.		N	Г				
			Perip	neral	Nerve	Funct	lion			
MDNS									10	3J
CSP									15	s Hospital
QSART									15	
Nerve Excitability									15	cent,
Nerve Conduction									15	St Vincent'
Systemic Health] []	
Fasting blood test									10	

5. Response measures and summary of data collection methods

5.1. Efficacy measures:

5.1.1. Primary efficacy measures:

PrimaryOutcome:

Central Corneal Nerve Fibre Length (CNFL) (measured in mm/mm² using a Heidelberg Rostock Tomographer III with corneal module,

quantified using a fully-automated method (ACCMetrics))

Timepoint: Change in CNFL from Day 1 at Days 90 +/- 14, 180 +/- 24

5.1.2. Secondary efficacy measures:

SecondaryOutcome:
Central Corneal Nerve Fibre Density (CNFD) (measured in mm/mm²
using a Heidelberg Rostock Tomographer III with corneal module,

using a Heidelberg Rostock Tomographer III with corneal module, quantified using a fully-automated method (ACCMetrics))

Timepoint: Change in CNFD from Day 1 at 90 +/- 14, 180 +/- 24

Secondary Central Corneal Nerve Branch Density (CNBD) (measured in

Outcome: mm/mm² using a Heidelberg Rostock Tomographer III with corneal

module, quantified using a fully-automated method (ACCMetrics))

Timepoint: Change in CNBD from Day 1 at Days 90 +/- 14, 180 +/- 24

SecondaryOutcome:

Central corneal thresholds to a room-temperature air stimulus (measured in mBar using a non-contact corneal aesthesiometer)

Timepoint: Change from Day 1 at Days 90 +/- 14, 180 +/- 24

Secondary Central corneal thresholds to a cooled stimulus (measured in mBar

Outcome: using a non-contact corneal aesthesiometer)

Timepoint: Change from Day 1 at Days 90 +/- 14, 180 +/- 24

Secondary Change in health state (index score and visual analogue score as

Outcome: measured using the EQ-5D-5L questionnaire). Timepoint: Change from Day 1 at Day 90 +/- 14, 180 +/- 24

Secondary Michigan Neuropathy Screening Score (MNSI) composite score

Outcome:

Timepoint: Change from Day 1 at Day 180 +/- 24

Secondary Michigan Diabetic Neuropathy Score (MDNS) (measured through

Outcome: clinical examination)

Timepoint: Change from Day 1 at Day 180 +/- 24

Secondary Routine nerve conduction studies (NCS) –sural sensory amplitude

Outcome: (measured using Dantec Keypoint G4 Workstation)

Timepoint: Change from Day 1 at Day 180 +/- 24

Secondary Routine nerve conduction studies (NCS) – peroneal motor velocity

Outcome: (measured using Dantec Keypoint G4 Workstation)

Timepoint: Change from Day 1 at Day 180 +/- 24

Routine nerve conduction studies (NCS) - tibial motor minimum F-**Secondary** Outcome: wave latency (measured using Dantec Keypoint G4 Workstation)

Timepoint: Change from Day 1 at Day 180 +/- 24

Nerve excitability profile: Depolarising threshold electrotonus (TEd) **Secondary** Outcome: (peak), TEd (90-100 ms), hyperpolarising threshold electrotonus

> (Teh) (90-100 ms), TEd (10-20 ms), superexcitability, subexcitability, resting current-voltage (I/V) slope, strength duration time constant

(measured with QTRAC software using TROND protocol)

Timepoint: Change from Day 1 at Day 180 +/- 24

Secondary Quantitative sudomotor axonal reflex testing (QSART), measured at

Outcome: the foot in sweat volume in nL using the QSWEAT system.

Timepoint: Change from Day 1 at Day 180 +/- 24

Secondary Cutaneous silent period testing: upper and lower limb (measuring

Outcome: silent period onset latency and duration) Timepoint: Change from Day 1 at Day 180 +/- 24

5.2. Safety measures:

Safety Outcome: Adverse events (AEs) reported

Timepoint: Change from Day 1 at Days 30 +/- 14, 90 +/- 14, 180 +/- 24

Safety Outcome: Change in habitual visual acuity measured using a standard eye chart

Timepoint: Change from Day 1 at Days 30 +/- 14, 90 +/- 14, 180 +/- 24

Change in intraocular pressure (IOP) measured using a Goldmann **Safety Outcome:**

tonometer

Timepoint: Change from Day 1 at Day 180 +/- 24

Safety Outcome: Diabetic retinopathy graded using the Wisconsin Scale grading system

Change from Day 1 at Day 180 +/- 24

Secondary Blood samples (measuring fasting glucose, fasting lipid profile [LDL, **Outcome:**

HDL, total cholesterol, triglycerides], FBC, ESR, CRP, Vitamin B-12,

Folate, TSH, UEC, HbA1c, liver function, electrolytes)

Timepoint: Change from Day 1 at Day 180 +/- 24

5.3. Compliance measures:

Compliance Total omega-3 status obtained from blood finger spot test (Waite

Outcome: Lipid Analytical Services)

Change from Day 1 at Day 180 +/- 24 Timepoint:

Compliance Total omega-9 status obtained from blood finger spot test (Waite

Outcome: Lipid Analytical Services)

Timepoint: Change from Day 1 at Day 180 +/- 24

Timepoint:

Compliance Total omega-6 status obtained from blood finger spot test (Waite

Outcome: Lipid Analytical Services)

Timepoint: Change from Day 1 at Day 180 +/- 24

Compliance Omega-6:Omega-3 ratio obtained from blood finger spot test (Waite

Outcome: Lipid Analytical Services)

Timepoint: Change from Day 1 at Day 180 +/- 24

Exploratory outcome measures:

1. Compliance outcome: supplement count at Day 180 +/- 24

- 2. Efficacy of masking: Guessing of treatment at Day 180 +/- 24
 - Guessing by participant
 - Guessing by examiner
- 3. Change in central corneal dendritic cell count (CDC) (measured in cells/mm2 using a Heidelberg Rostock Tomographer III with corneal module) from Day 1 at Days 90 +/-14, 180 +/- 24
- 4. Change in peripheral corneal nerve fibre length (CNFL) (measured in mm/mm2 using a Heidelberg Rostock Tomographer III with corneal module) from Day 1 at Days 90 +/- 14, 180 +/- 24
- 5. Change in peripheral corneal dendritic cell count (CDC) (measured in cells/mm2 using a Heidelberg Rostock Tomographer III with corneal module) from Day 1 at Days 90 +/- 14, 180 +/- 24
- 6. Change in peripheral corneal thresholds to a room air stimulus (measured in mBar using a non-contact corneal aesthesiometer) from Day 1 at Days 90 + /- 14, 180 + /- 24
- 7. Change in peripheral corneal thresholds to a cooled stimulus (measured in mBar using a non-contact corneal aesthesiometer) from Day 1 at Days 90 +/- 14, 180 +/- 24
- 8. Routine nerve conduction studies (NCS) ulnar sensory amplitude, velocity and latency (measured using Dantec Keypoint G4 Workstation) from Day 1 at Day 180 +/- 24
- 9. Routine nerve conduction studies (NCS) median sensory velocity, amplitude and latency (measured using Dantec Keypoint G4 Workstation) from Day 1 at Day 180 +/-24
- 10. Routine nerve conduction studies (NCS) sural sensory velocity and latency (measured using Dantec Keypoint G4 Workstation) from Day 1 at Day 180 +/- 24
- 11. Routine nerve conduction studies (NCS) median motor velocity, amplitude and latency (measured using Dantec Keypoint G4 Workstation) from Day 1 at Day 180 +/- 24
- 12. Routine nerve conduction studies (NCS) tibial motor amplitude and latency (measured using Dantec Keypoint G4 Workstation) from Day 1 at Day 180 +/- 24

- 13. Routine nerve conduction studies (NCS) peroneal motor amplitude and latency (measured using Dantec Keypoint G4 Workstation) from Day 1 at Day 180 +/- 24
- 14. Change in sweat volume in the forearm measured using quantitative sudomotor axonal reflex testing (QSART) from Day 1 at Day 180 ± 14
- 15. Change in sweat volume in the proximal leg measured using quantitative sudomotor axonal reflex testing (QSART) from Day 1 at Day 180 ± 14
- 16. Change in sweat volume in the distal leg measured using quantitative sudomotor axonal reflex testing (QSART) from Day 1 at Day 180 ± 14
- 17. Change in nerve excitability profile (additional parameters) from Day 1 at Day 180 ± 14
 - Stimulus (mA) for 50% max response
 - Rheobase (mA)
 - Stimulus-response\slope
 - Peak response\(mV\)
 - Minimum I/V slope
 - Temperature (°C)
 - RRP (ms)
 - Polarizing current\(% threshold)
 - Polarizing current\(mA)
 - Latency (ms)
 - TEd(40-60ms)
 - TEh(10-20ms)
 - TEd(undershoot)
 - TEh(overshoot)
 - S2 accommodation
 - Accommodation half-time (ms)
 - Hyperpol. I/V slope
 - Refractoriness at 2.5ms (%)
 - TEh(20-40ms)
 - TEh(slope 101-140ms)
 - Refractoriness at 2 ms (%)
 - Superexcitability at 7 ms (%)
 - Superexcitability at 5 ms (%)
 - TEd20 (peak)
- 18. Change in dry eye symptoms (measured using the validated Ocular Surface Disease Index (OSDI) questionnaire) from Day 1 at Days 90 +/- 14, 180 +/- 24
- 19. Change in tear stability measured using corneal sodium fluorescein from Day 1 at Days 90 + -14, 180 + -24
- 20. Change in tear osmolarity: electrolyte concentration of the tears (measured in mOsm/L using the TearLab system (TearLab Corporation Pty Ltd) from Day 1 at Day 180 +/- 24

- 21. Change in tear production measured using the phenol red thread test (R+L) from Day 1 at Days 90 + /- 14, 180 + /- 24
- 22. Additional slit lamp microscopy grading
 - Blepharitis grading from 0 4
 - Meibomian gland dysfunction grading (MGD) from 0 4
 - Conjunctival redness grading from 0 4
 - Limbal redness grading from 0 4
- 23. Change in corneal sodium fluorescein (NaFl) staining score, as the average of two eyes, from Day 1 at Day 90 + /- 14, Day 180 + /- 24
 - Corneal staining graded from 0 4
- 24. Change in tear composition markers from Day 1 at Day 180 +/- 24
- 25. Change in indirect healthcare costs measured using the iMTA-iPCQ health economics questionnaire at Day 1 and Day 180
- 26. Change in ONH structure retinal neuro-retinal fibre layer (RNFL) thickness in the right eye measured using Optic Coherence Tomography (OCT) from Day 1 at Day 180 +/- 24
- 27. Change in macular thickness in the right eye measured using Optical Coherence Tomography (OCT) from Day 1 at Day 180 +/- 24
- 28. Change in foveal avascular zone area in the right eye, measured using Optical Coherence Tomography Angiography (OCT-A) from Day 1 at Day 180 +/- 24
- 29. Change in retinal vascular calibre in the right eye, measured using Optical Coherence Tomography Angiography (OCT-A) from Day 1 at Day 180 +/- 24

6. Methods of data collection and study reports

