7.3. Adverse events (AEs)

7.3.1. Assessments and documentations of adverse events

All AEs and SAEs will be immediately (within 24 hours) reported to the Principal Investigator by the research team member.

At Visit 1, after informed consent and before the initial study products are administered, all pretreatment adverse events will be documented (e.g., allergic response to topical anaesthetic). Conditions that are present at screening and do not deteriorate will not be considered adverse events.

After the study product supply, all treatment-emergent post-treatment adverse events will be documented. Abnormal laboratory values will not be considered adverse events unless deemed clinically significant by the medical monitor, and documented as such.

If adverse events occur, the first concern will always be the safety of the study participants. All adverse events, including severity, action taken and likely relationship to the study product will be documented throughout the study.

At each visit, the co-investigator or principal investigator will begin the examination by querying for adverse events by asking each participant a general, non-directed question such as "How have you been feeling since the last visit?" Directed questioning and examination will then be carried out as appropriate.

The description of each AE recorded will include:

- A description of the AE;
- The onset date, duration, date of resolution;
- Severity (assessed as per section 7.4;
- Seriousness (i.e., is it an SAE?);

nPROOFS1-v1.2 [01-July-2018] Page 23 of 53

- Actions taken;
- The outcome;
- The likelihood of the relationship of the AE to the study treatment (Unrelated, Possible, Probable, Definite).

For each adverse event reported, the number and percent of participants affected will be tabulated. Separate adverse event tables will be generated for pre-treatment AEs and post-treatment AEs. All adverse events will be presented in the listings. Other safety variables, including biomicroscopy findings, BCVA, IOP, retinal fundus photograph and blood test results will be analysed.

DEFINITIONS:

• An adverse event is **any** untoward medical occurrence in a participant or clinical investigation of participant administered a pharmaceutical product. It does not necessarily have a causal relationship with treatment.

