11.3 Basic blood samples

Blood tests to assess diabetes control will be performed, including fasting blood sugar level and HbA1c. Patients that have any disorder other than diabetes that could cause symptoms or signs of peripheral neuropathy will be excluded from participating. Thus, participants will be tested for B12 levels, folate levels, lipid profile, inflammatory markers (CRP, ESR), liver function and electrolytes.

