To evaluate the effects of a six-month supplementation period with oral long-chain omega-3 PUFA supplements on peripheral nerve health in individuals with type-1 diabetes, as measured by the change from baseline in central corneal nerve fibre length (CNFL) at day 180.

Aim 2

To evaluate the effects of a six-month supplementation period with oral long-chain omega-3 PUFA supplements in individuals with type-1 diabetes on the change from baseline at day 180 for:

Key secondary outcomes:

Other corneal nerve structure and function parameters

[2 main variables for corneal nerve structure: central corneal nerve branch density (CNBD) and central corneal nerve fibre density (CNFD)

2 main variables for corneal nerve function: central corneal sensitivity thresholds to room and cooled temperatures]

Secondary outcomes:

- Patient-reported quality of life

[2 main variables: EQ-5D-5L VAS and Index]

- Small nerve fibre function

[6 main variables: CSP onset latency and duration in the upper limb, CSP onset latency and duration in the lower limb, QSART sweat volume and latency in the foot]

- Large nerve fibre function

[2 symptom/clinical sign composite score variables: MNSI and MDNS (clinical examination) scores]

[3 main neurophysiology variables: sural SNAP amplitude, peroneal motor conduction velocity and tibial minimum F-wave]

- Median nerve excitability

[8 main variables: Depolarising threshold electrotonus (TEd) (peak), TEd (90-100 ms), hyperpolarising threshold electrotonus (Teh) (90-100 ms), TEd (10-20 ms), superexcitability, subexcitability, resting current–voltage (I/V) slope, strength duration time constant]

Aim 3

To evaluate the safety of a six-month supplementation period with oral long-chain omega-3 PUFAs in individuals with type-1 diabetes, by evaluating the incidence of adverse events, change in habitual distance visual acuity, change in intraocular pressure, change in diabetic retinopathy grading, and change in blood pathology parameters from baseline at day 180.

3. Analysis sets/Populations

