- 11. Scheduled or planned ocular surgery over the course of the study;
- 12. Any history of rigid contact lens wear;
- 13. Grading of diabetic retinopathy worse than 'moderate' in either eye according to the simplified ETDRS (Wisconsin) classification (ETDRS Research Group 1991);
- 14. Presence of any of the following ocular conditions: active ocular infection or inflammation that in the judgment of the investigator may interfere with the interpretation of the study results;
- 15. Corneal abnormalities or damage that could disrupt normal corneal nerve morphology, including keratoconus, bullous keratopathy, advanced corneal dystrophies, history of neurotrophic keratopathy including herpes keratitis and severe Sjogren's associated dry eye disease;

- 16. History of refractive surgery or trauma within the past 12 months;
- 17. Use of autologous serum eye drops within the past three months, or their anticipated use during the course of the study;
- 18. Participant has a medical or ocular condition, or is in a situation, which in the principal investigator's opinion, may put the participant at significant risk, may confound the study results, or may interfere significantly with participation in the study.

Interventional

- 19. Current or previous regular consumption of any omega-3 oral supplements (>3 times/week) in the past three months;
- 20. Current participation in another interventional drug or device study or anticipated entry into such a study within one month of enrolment;
- 21. Known allergy or hypersensitivity to any components of the study supplements;
- 22. Cultural or religious beliefs that exclude the consumption of certain or all animal products.

4. Endpoints and Covariates

All variables are listed in Appendix 1 and the definition of the derived variables can be found in Appendix 2.

5. Handling of Missing Values and Other Data Conventions

During data collection, regular verification of the source documents was undertaken to minimise the potential for missing data. Data collected outside the specified time windows for each study visit will be set to missing (see Table 1 in Section 10). The number and percentage of missing data will be calculated for each of the outcomes listed in Appendix 1.

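### Fasting glucose, ESR and CRP are protocol-specified safety bloods with no row in the SAP's variable list, so following the SAP leaves them unanalysed and unexplained

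*Combined protocol and SAP*

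**What the plan says.** **Protocol.** Section 5.2 (Safety measures) has one entry for blood samples, timed as change from Day 1 at Day 180. It opens "Blood samples (measuring fasting glucose, fasting lipid profile [LDL", continues "HDL, total cholesterol, triglycerides], FBC, ESR, CRP, Vitamin B-12" and ends "Folate, TSH, UEC, HbA1c, liver function, electrolytes". The entry is labelled a secondary outcome but sits in the safety section. Section 7.1 counts basic blood tests at Visits 2 and 5 among the safety measures. Section 7.3.1 commits to analysis: "Other safety variables, including biomicroscopy findings, BCVA, IOP, retinal fundus photograph and blood test results will be analysed". Section 11.3 confirms the tests: "Blood tests to assess diabetes control will be performed, including fasting blood sugar level and HbA1c". It also names CRP and ESR as inflammatory markers to be tested.

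**SAP.** Aim 3 covers "change in blood pathology parameters from baseline at day 180" and names no analytes. The data source list in section 1 is equally general. Section 4 then fixes the variable set: "All variables are listed in Appendix 1". Appendix 1 has 21 blood rows. None is fasting glucose, ESR or CRP.

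**The concern.** The protocol sets a defined change endpoint for three named analytes and promises analysis of the blood results. The SAP gives those analytes no variable. Aim 3's general wording does not repair this, because Appendix 1 is declared to be the whole list.

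The safety aim concerns people with type-1 diabetes, and section 11.3 names fasting glucose and HbA1c together as the measures of diabetes control. Protocol 1.2 rests on an anti-inflammatory rationale and justifies olive oil as a control without effect on inflammatory mediators. CRP and ESR bear on both premises. A reader who compares protocol with report would find three pre-specified outcomes unaccounted for. Any general statement about blood safety would then rest on a narrower set than the protocol promised.

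**Working it through.** There is no plan figure to reproduce, because the point concerns missing items. The check is a cross-match of lists.

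**1. Protocol items against Appendix 1.** Counting each lipid separately, protocol 5.2 names 15 items or panels.

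| Protocol 5.2 | SAP Appendix 1 rows |
|---|---|
| Fasting glucose | none |
| LDL | LDL |
| HDL | HDL |
| Total cholesterol | cholesterol |
| Triglycerides | triglycerides |
| FBC | haemoglobin, platelets, white cells |
| ESR | none |
| CRP | none |
| Vitamin B-12 | vitamin B-12 |
| Folate | folate |
| TSH | TSH |
| UEC | creatinine, eGFR, sodium, potassium |
| HbA1c | HbA1c in mmol/mol and in % |
| Liver function | ALT, total bilirubin, ALP, GGT |
| Electrolytes | sodium, potassium, CO2 |

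Matched: 12. Unmatched: 15 − 12 = 3, namely fasting glucose, ESR and CRP.

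**2. Is there another route to analysis?** The SAP's Table 5 template has 7 blood rows: HbA1c (mmol/mol), cholesterol, HDL, LDL, creatinine, B-12 and folate. Supplementary Table S10 has 14: haemoglobin, platelets, HbA1c (%), ALP, sodium, potassium, CO2, TSH, white cells, triglycerides, ALT, total bilirubin, GGT and eGFR. The two sets do not overlap, and 7 + 14 = 21, which are exactly the 21 Appendix 1 rows. Appendix 1 therefore worked as the list from which the blood tables were filled. An analyte left off it had no planned route to analysis.

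**3. Were the three only entry tests?** Section 11.3 links the tests to excluding other causes of neuropathy. The same sentence names B-12, folate, lipids, inflammatory markers, liver function and electrolytes. Every one of these has Appendix 1 rows except the inflammatory markers. Section 5.2 also gives the whole list a Day 180 change. An entry purpose therefore does not explain why these were left out.

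**The case against.** The strongest reply is that this is a small documentation mismatch. The analytes are neither primary nor key secondary, HbA1c is analysed, and white cell count is listed. Laboratory values judged clinically significant are recorded as adverse events under protocol 7.3.1. All of that stands and limits the weight of the point. It does not give the three analytes a variable or a reason for their absence.

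A reader might infer more than the documents support:

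- **Selective reporting.** Protocol 8.1 requires the SAP to be final before unmasking, and Appendix 3 speaks of unmasking as still to come. Nothing shows that results drove the omission.
- **Silence in the list of changes from the planned analysis.** That list covers departures from the SAP. Analytes never in the SAP would not appear there.
- **Absence from Table S10 as proof of non-reporting.** S10 also lacks cholesterol, HDL, LDL, creatinine, B-12 and folate, so it supplements another blood table that is not in these documents. What that table contained cannot be checked.
- **Absence from Appendix 3 and Table 5.** Appendix 3 covers main outcomes. Both carry 7 blood rows and omit 13 other analytes that S10 reports. Absence there adds nothing.
- **Urea.** The protocol never names it, UEC is not expanded, and the panel has other rows.
- **CRP and ESR as the only inflammation measures.** White cell count is also listed, so this is too strong.

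**Conclusion.** The point holds for fasting glucose, ESR and CRP: 3 of 15 protocol-named blood items have no row in a list the SAP calls complete. This is a contradiction between protocol and SAP, not merely missing detail, because the protocol names the analytes, sets their time point and says blood results will be analysed. Its weight is modest. It does not touch the primary or key secondary analyses, and glycaemic control is partly covered by HbA1c.

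The conclusion assumes that Appendix 1 is the full variable list, as SAP section 4 says and as the 7 + 14 = 21 match supports. It makes no assumption about intent. It also makes none about whether the values exist. Table S10 shows that bloods were incomplete: placebo 19 of 22 at baseline and 16 at Day 180, against 21 and 20 of 21 in the omega-3 arm.

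**What to change.** Add fasting glucose, ESR and CRP to Appendix 1 and to the supplementary blood safety table (Table S10 as issued), in the Safety sample. Use the repeated measures model already planned for bloods at days 1 and 180, on the log scale if the distribution is skewed, as was done for other skewed bloods. Label the rows as specified in the protocol but omitted from the SAP, so that readers know their status. Rows in Appendix 3 or Table 5 are not needed.

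If an analyte was not obtained, or was dropped on purpose, replace the row with a statement of that, the reason and the number missing in each arm.

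Where the values exist, the cost is three more rows from an existing model, with no new visits. The statistical downside is three more unadjusted safety comparisons. If there were no true effects, they would add 3 × 0.05 = 0.15 expected false positives. The SAP already reports such p-values unadjusted and with caution.
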